8.2 Secondary endpoints

- The time to the onset of clinical symptoms of a respiratory infection with positive SARS-CoV-2 PCR from the moment of the first contact with COVID-19;
- Time to a positive swab PCR SARS-CoV-2;
- Number of symptomatic cases of SARS-CoV-2 infection in both study groups;
- The number of mild, moderate and severe forms of COVID-19;
- The presence and type of side effects of Bromhexine hydrochloride

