8.3 Methods for assessing primary and secondary endpoints

1. Clinical assessment of study participants for the presence of symptoms of respiratory infection

- 2. Laboratory diagnostics of the presence of SARS-CoV-2: swab PCR test;
- 3. Chest computed tomography, pulse oximetry to assess the severity of the disease;

4. Laboratory diagnostics of SARS-CoV-2 infection: plasma IgG;

5. Laboratory diagnostics of the severity of COVID-19: clinical blood test with leukocyte count, C-reactive protein, D-dimer, ALT, AST, bilirubin fraction; creatinine, urea, protein fractions; amylase; glucose;

6. The need for oxygen support and its type in the treatment of COVID-19; the duration of the need for oxygen therapy; duration of mechanical ventilation.

7. Working hours (hours) with patients with confirmed / suspected SARS-CoV-2 infection;

8. Additional observation of all study participants up to 8 weeks from the date of randomization.

Methodology for calculating the time of work with SARS-CoV-2 infection

1. Units of time calculation - hours;

2. Separately taken into account: a) the time of work in the therapeutic department, including the emergency room where patients with suspected / confirmed SARS-CoV-2 infection are located; b) the time of work in the intensive care unit, where patients with suspected / confirmed SARS-CoV-2 infection are located; c) the time of work in a "clean" area, outside the presence of patients with suspected / confirmed SARS-CoV-2 infection;

3. Working hours in the hospital without personal protective equipment in accordance with the regulations of Almazov National Medical Research Centre.

9. Randomization and sample size estimation

Randomization method: 1:1, allocation by minimization method to the preventive therapy group with Bromhexine hydrochloride and to the control group, taking into account the following factors: age (ranges 18-45, 45-64, 65-74, 75-79); type of contact with SARS-CoV-2 infection: ("red zone"; "green" zone); taking hydroxychloroquine to prevent COVID-19.

• "Red" zone: the closest and longest contact with SARS-CoV-2 infection associated with an infected aerosol (work in intensive care units and intensive care units; in operating and intervention laboratories; work with biological material of infected patients);

• Green Zone: work outside direct contact with patients with confirmed / suspected SARS-CoV-2 infection.

Known statistics:

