• The presence of side effects of the use of Bromhexine hydrochloride, which complicates its further safe use and / or any other intolerance to the drug;

- The onset of pregnancy;
- Suspected / confirmed SARS-CoV-2 infection;
- Period of disability and / or hospitalization associated with SARS-CoV-2 infection.

13. Replacement of subjects when excluded from the study

Participants excluded from the study will not be replaced.

14. Preliminary study termination

The study may be terminated prematurely if there is a significant difference in the safety endpoints between groups after enrollment of 20 subjects, which indicates unacceptable safety. If the superiority of the treatment method is found early, there will be no reason for early termination of the study.

15. Safety reports

15.1 Adverse events (AE).

Adverse event is any unwanted event that may occur to a study subject during the study course, whether or not associated with bromhexine hydrochloride treatment. All adverse events reported by an investigator should be recorded.

Examples of adverse events based on studies in patients taking bromhexine:

Significant: allergic reaction in the form of anaphylactic shock;

Minor: nausea, vomiting, diarrhea, allergic reaction in the form of urticaria

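### The Section 14 safety stop compares the groups on safety endpoints, but the only safety item in Section 8.2 is bromhexine side effects, which controls cannot have by definition

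*Combined protocol and SAP*

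**What the plan says.** Section 14 permits early termination "if there is a significant difference in the safety endpoints between groups after enrollment of 20 subjects", on condition that the difference shows safety to be unacceptable. It does not name those endpoints. It also says that early evidence of superiority would not be a reason to stop.

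Section 8.2 lists one safety item: "The presence and type of side effects of Bromhexine hydrochloride".

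Section 15.1 is wider. It defines an adverse event (AE) for any study subject, "whether or not associated with bromhexine hydrochloride treatment", and adds: "All adverse events reported by an investigator should be recorded". Section 15.2 defines serious adverse events (SAEs) and requires immediate reporting. Neither section is named as an endpoint, and Section 14 refers to neither.

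Section 15.1 also uses the key word of the stopping rule in a clinical sense: "Significant: allergic reaction in the form of anaphylactic shock".

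**The concern.** A between-group comparison needs a quantity that can be counted in the same way in both groups. The Section 8.2 item is defined by exposure to bromhexine, so the control count is zero before any data are seen. Section 3 describes an open-label design, so whoever attributes a complaint knows the arm. The minor events given as examples in Section 15.1 (nausea, vomiting, diarrhea, urticaria) also occur without the drug. A background complaint can therefore enter the treated count and never the control count.

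The direction of the bias is towards apparent harm, and it does not shrink with sample size: more participants only make the artificial difference easier to declare significant. At stake is the safety half of the aim in Section 2, and whether anyone applying Section 14 has a meaningful comparison to judge.

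The trigger is also open in two respects. It may mean one look at 20 participants or any time from then on, and *significant* may be statistical or clinical.

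**Working it through.** **Inputs.** Allocation is 1:1 (Section 9), so 20 enrolled is about 10 v 10. The later size of 40 v 40 is chosen for illustration. Section 9 states a 5% alpha for the primary sample size only; applying it two-sided to safety is an assumption. All event rates are assumptions: Section 1 calls nausea common but gives no rate, and the figure of 0.16 per million concerns severe reactions.

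**The plan's own figures.** The safety rule has no figure except the 20. The sample size reproduces: (1.960 + 0.842)² × (0.3 × 0.7 + 0.1 × 0.9) / 0.2² = 58.87, so 59 per group and 118 in all; 118 / 0.85 = 138.8, so 139. It is not at issue here.

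**Step 1: events needed when controls count zero.** For *x* of *n* against 0 of *n*:

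- Fisher, two-sided: p = 2 × C(n, x) / C(2n, x).
  - n = 10: x = 4 gives 0.087 and x = 5 gives 0.033, so 5 are needed.
  - n = 40: x = 5 gives 0.055 and x = 6 gives 0.026, so 6 are needed.
- Chi-square, uncorrected: X² = 2n·x / (2n − x).
  - n = 10: x = 3 gives 60/17 = 3.53 (p = 0.060) and x = 4 gives 80/16 = 5.00 (p = 0.025), so 4 are needed.
  - n = 40: x = 3 gives 240/77 = 3.12 (p = 0.077) and x = 4 gives 320/76 = 4.21 (p = 0.040), so 4 are needed.

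**Step 2: a harmless drug on the Section 8.2 item.** The treated count is binomial(n, q), where q is the share with an attributed background complaint. The chance of significance is P(X ≥ threshold).

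**Step 3: a harmless drug on all-cause AEs.** Both counts are binomial at the same rate. The probabilities of all tables significant in the harm direction are summed.

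| Comparison | Rates, treated v control | 10 v 10, Fisher / chi-square | 40 v 40, Fisher / chi-square |
|---|---|---|---|
| Attributed side effects | 10% v 0 | 0.2% / 1.3% | 21% / 58% |
| Attributed side effects | 20% v 0 | 3.3% / 12% | 84% / 97% |
| All-cause AEs | 20% v 20% | 0.4% / 1.5% | 1.4% / 2.6% |

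In the last two rows the drug and the treated arm's 20% rate are the same. Only the endpoint definition differs.

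**Step 4: what one look at 10 v 10 can show.** With no events in 10, the exact 95% upper limit is 1 − 0.025^(1/10) = 0.308, or 31%. A true all-cause excess of 30% v 10% is significant 5.7% (Fisher) or 14% (chi-square) of the time, and 28% with a one-sided uncorrected test.

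**The case against.** The strongest reply is that AEs are plainly meant. Section 14 speaks of endpoints in the plural, compared between groups, and Sections 15.1 and 15.2 follow directly with definitions covering every subject. On that reading the fault is a missing cross-reference. This has force, and it rules out one inference a reader might draw, that the trial collects no comparable safety data. It does collect them. But nothing in the text makes them the endpoint, and the endpoint list names something else.

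A reader might also infer that a harmless drug would be stopped 84% to 97% of the time. The documents do not support that. Section 14 says the study may be ended, and the difference must also indicate unacceptable safety. An excess of complaints that Section 15.1 itself classes as minor need not meet that condition. The rates are also assumed, and at 10 v 10 the same scenario gives only 3.3% / 12%.

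A third tempting reading is that repeated looks leave error seriously uncontrolled. With equal AE rates of 10% to 30%, six looks (every 20 up to 100, then 118) give false harm signals in 2.2–4.1% (Fisher) or 6.6–7.4% (chi-square), against 1.1–1.6% or 2.5–2.7% for one test at 118. For a discretionary harm rule that is modest. The efficacy error is not inflated by early stopping for benefit, since Section 14 excludes superiority as a reason to stop.

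Finally, SAE reporting, daily clinical follow-up and individual withdrawal protect participants whatever Section 14 means. That limits the severity but does not supply a like-for-like comparison.

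**Conclusion.** The concern holds as a mismatch between Sections 8.2 and 14. The only listed safety item cannot be compared between the groups without bias towards harm, and the all-cause data that could be compared are not linked to the rule. The bias can be large for a p-value (84% / 97% against 1.4% / 2.6% at 40 v 40 with a 20% rate), but its effect on an actual decision cannot be quantified, because that decision rests on judgement.

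This depends on controls not receiving bromhexine, which the allocation in Section 9 implies although the design figure is not available here, and on the assumed rates. The unstated number of looks and the unstated sense of *significant* are secondary gaps. A quiet single look at about 10 v 10 should not be taken as reassurance. Severity: minor to moderate.

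**What to change.** **Section 8.2.** Define the safety endpoint as all AEs and SAEs in both arms, with bromhexine-attributed effects as a descriptive subset. Count everyone randomized, from randomization to the end of the 8-week observation or last contact. This matters for three reasons:

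- Section 12 withdraws participants for "The presence of side effects of the use of Bromhexine hydrochloride, which complicates its further safe use", which can happen only in the treated arm, and Section 13 adds: "Participants excluded from the study will not be replaced".
- Table 1 marks bromhexine at 5–8 weeks, so a 28-day cut-off would miss events during scheduled dosing.
- Section 8.3 already plans the follow-up: "Additional observation of all study participants up to 8 weeks from the date of randomization".

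Because the AE definition is broad enough to include COVID-19 itself, show primary-endpoint events on a separate line, so that a benefit does not mask other harm.

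**Section 14.** Refer to this endpoint and tabulate it by arm with exact confidence intervals. State whether the rule means one look or several, and whether *significant* is statistical or clinical. The threshold and schedule remain the sponsor's decision. Immediate SAE reporting is unchanged.

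**Cost.** Wording in two sections and short tables of events already recorded, with no extra visits or participants. All-cause counting reduces attribution bias but does not remove differences in reporting between open-label arms, so the same AE questions should be put to both.

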15.2 Severe adverse events (SAE)

SAE – is any unwanted event, which in any from or duration may: - cause death;

- is life-threatening (when it develops);
- requires unscheduled hospitalization or prolongs hospitalization period;

- leads to permanent or severe disability;

- any other important medical event that does not lead to death, is not life-threatening and does not require hospitalization, but may be interpreted (according to a specialist's opinion) as an event with risk to a subject or needs an additional medical intervention for the prevention of an event.

When SAE is expected, an investigator must immediately inform the study coordinator and the primary investigator. The study coordinator and primary investigator are responsible for notification of the ethics committee.

16. Ethics

The study will be conducted in accordance with the principles of the Declaration of Helsinki (version 59 review of the WMA article, Seoul, Korea, October 2008).

